Appendix A. Drugs Allowed (Y) and Drugs not Allowed (N) for Study Periods I and II

Drug Class	Episodic Use	Chronic Use
Alpidem	N	N
Amantadine	N	N
Analgesics (except narcotics)	Y	N
Anorexics	N	N
Antianginal agents (except calcium channel blockers)	Y	Y
Antiarrhythmics	N	N
Anticholinergics	Y	Y
Anticholinesterase inhibitors	N	N
Anticonvulsants	N	N
Antidepressants	N	N
Antidiarrheal preparations	Y	N
Antiemetics	Y	N
Antihypertensives	N	Y
Antipsychotics	N	N
Benzodiazepines	N	N
Buspirone	N	N
Carbamazepine	N	N
Chloral hydrate	N	N
Clonidine	N	N
Codeine	Y	N
Cough/Cold preparations	Y	N
Cyclosporine	N	N
DHEA	N	N
Ginko	N	N
Ginseng	N	N
Guanfacine	N	N
Loperimide	Y	N
Methyldopa	N	N
Metyrosine	N	N
Narcotics	N	N
Phenytoin	N	N
Pimozide	N	N
Prazosin	N	N
Psychostimulants	N	N
Quinidine	N	N
Reserpine	N	N
Rifampin	N	N
St. John's Wort	N	N
Steroids (oral)	Y	N
Thyroid hormone supplement ^a	N	Y
Tryptophan	N	N

^aSubjects needing supplements must be on a stable thyroid supplement dose for at least 2 weeks prior to Visit 1.

Subjects may use zolpidem, eszopiclone, zaleplon, or diphenhydramine up to 3 nights per week during the trial.

Updated **January 22, 2019**

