3. Specific Aim 3 (Secondary Aim): To determine the efficacy of Vortioxetine in reducing depressive symptoms in PTSD patients.

Hypothesis: PTSD patients randomized to acute therapy with Vortioxetine will show more improvement in depressive symptoms compared to subjects randomized to placebo, as determined by mean changes in the Montgomery-Asberg Depression Rating Scale (MADRS) score over the course of 12 weeks.

4. Exploratory Aim 1: Startle: To assess fear potentiation, conditional discrimination (AX+/BX-), and fear inhibition using acoustic startle methodology in a classical conditioning paradigm in PTSD patients before and after treatment with Vortioxetine.

Hypothesis: PTSD subjects randomized to 12 weeks of Vortioxetine will have improved fear inhibition as measured by the AX+/BX- paradigm compared to baseline, while placebo subjects will not show improvement.

5. Exploratory Aim 2: Cognition, Functional Capacity, and Quality-of-Life: To assess neurocognitive performance (pre- and post-treatment) with tests shown to be sensitive to PTSD (e.g. learning and memory, concentration and attention, and executive functioning). In addition, to explore performance-based measures of everyday living skills, and measure quality-of-life as indexed by subjective reports.

Hypothesis: Statistically significant changes detected for these variables will be correlated across domains.

6. Exploratory Aim 3: Genotyping and Gene Expression: To explore whether response to Vortioxetine is associated with certain candidate gene polymorphisms previously associated with PTSD, and whether treatment with Vortioxetine alters gene expression patterns differentially in treatment responders and non-responders.

Hypothesis: Polymorphisms of specific candidate genes previously identified as relevant to PTSD will be differentially distributed between responders and non-responders to vortioxetine.

III. SIGNIFICANCE/BACKGROUND

Significance of PTSD and Limitations of Current Pharmacotherapies

PTSD is a common chronic anxiety disorder that is often debilitating and follows exposure to an overwhelming traumatic event. PTSD occurs in approximately 8%-14% of the U.S. population (Breslau et al 1998; Davidson et al 1991; Kessler et al 1995). Rates of PTSD among women in the US are higher than in men being approximately twice that of men 12%-18% (Breslau et al 1998; Resnick et al 1993).

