(1) Screening Phase and (if necessary) Medication-Washout: Informed consent will be signed at the initiation of the screening phase. As part of the informed consent process, participants will be asked whether they are willing to have their research assessments videotaped, and to indicate their authorization for Audio/Video/Photography Recording on the

consent form. Patients refusing to consent to videorecording will still be permitted to participate in the study. Recordings of study visits will be used by the study team for interrater reliability training and assessment. Screening for psychiatric and medical eligibility will involve vital signs, weight, blood tests, pregnancy test, drug screen, psychiatric interviews, medical and psychiatric history, physical exam and electrocardiogram (EKG). We will also draw the genotype sample at this visit for consenting subjects.

If a patient is already taking medication for PTSD and has achieved therapeutic response, s/he will not be tapered off the effective medication(s) to participate in this study, and will not be eligible for the study. Patients who are taking a psychotropic medication that has proven ineffective for their PTSD symptoms will be tapered off the medication prior to randomization. Whenever possible, decisions to taper a patient's medication for the purpose of study participation will be made in conjunction with the patients' prescribing physician. Patients will be tapered off ineffective psychotropic medications over 7-21 days, though patients on fluoxetine or protriptyline will be required to be off those medications for 5 weeks prior to baseline. Risks associated with medication tapering will be discussed with the patient. This washout process will be conducted and monitored by the study physician.

(2) Study Period I – Pretreatment Testing (Days –7 to –1): Visit 1. During this study period, subjects will undergo surrogate marker testing (psychophysiology, and neuropsychological testing). These visits will be conducted over a 7-day period prior to the day of randomization, following the successful completion of all the screening procedures in Phase 1 above. We anticipate that these procedures can be completed in 1 study visit; however, we will be flexible to allow additional visits if required due to subject fatigue or time constraints.

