3) Study period II Treatment (Day 0 to 84): Visits 2 through 9. This is the 12-week period of double-blind placebo-controlled acute treatment. At day 0, EKG for safety monitoring will be conducted. The baseline mRNA sample will be collected. All subjects who continue to meet eligibility criteria will be randomized to one of two groups: Vortioxetine or placebo. Randomization will be performed at a 1:1 ratio into two treatment groups, and both vortioxetine and placebo will be distributed to the patient in blister packs. If a participant is taking 10mg of vortioxetine they will be provided with 2 blister packs at each visit. If a participant is taking 20mg, they will be provided with 4 blister packs. Surrogate marker testing for psychophysiology, mRNA, and neuropsychological testing will be repeated at the completion of the double-blind treatment. Due to the amount of study procedures for certain study visits, we will allow study visits to be done over two days.

4) Follow-Up (Day 84 to 98): Visit 10. Patients will return to the clinic two weeks after the last dose of study medication for assessment of psychiatric status, suicidality, follow-up of any abnormal laboratory or EKG results, and to assist with transition of psychiatric care, if indicated.

See the **Schedule of Events** chart at the end of this section for details of the procedures performed during each visit.

B. Justification of Sample Size

Power Analysis:

Samples of n=60 (2 groups) are associated with reduced but adequate power. Between group differences in change scores of $d=.70$ are detectable with .80 power at $p<.05$. Correlations of

.33 between two variables are detectable with power=.80 in the full sample of 60. Within treatment conditions (n=30) correlations of $r=.50$ are detectable with the same level of power.

C. Informed Consent, Regulatory and Ethical Considerations

The study will be conducted in accordance with Good Clinical Practices (GCP), 21CFR Parts 50 and 56 and all applicable regulatory requirements. Approval for conduct of the study will be obtained from the institutional review boards at both sites.

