After patients consent to participate, they will undergo several procedures, which will occur over 1-2 visits. These include: (1) psychiatric interview by a research psychiatrist or psychologist; (2) a structured clinical interview (the Mini International Neuropsychiatric Interview, "MINI," Modules A and C through P); (3) administration of the CAPS-5, Columbia Suicide Severity Rating Scale (CSSRS), and Clinical Global Impression of Severity (CGI-S); (4) completion of several self-report instruments; (5) collection of blood samples for safety testing and genotype analysis, pregnancy testing (if indicated), urine sample [urinalysis, toxicological screen]; (6) EKG; and (7) physical examination.

A clinical researcher with specialized training in diagnostic assessment will perform the specified modules of the MINI and the rating scales. Appropriately trained study staff will conduct all medical tests and obtain biological samples for the following laboratories: blood samples for serum chemistries, liver function panel, free T4, thyroid stimulating hormone, hepatitis B surface antigen, hepatitis C antibody, serum pregnancy, gamma-glutamyl transferase (GGT), and complete blood count (CBC), urinalysis and urine drug screen. At the conclusion of the screening process, the patient will be contacted within several days regarding preliminary eligibility. All patients who are eligible will be scheduled for an in-person visit approximately one week after the initial evaluation. The participant will continue into Study

Period I at that time. If deemed ineligible for the protocol, a study physician will explain the reasons for disqualification, and these patients will receive appropriate research or treatment referrals. If symptoms worsen significantly during this period, as determined by the study physician's assessment, subjects will be removed from the study and given appropriate referrals after meeting with the study investigators. Options would include referral to the resident psychopharmacology clinic or referral back to their treating physician.

E. Study period I: Pre-Treatment Testing

During this testing phase, which will be scheduled within one week of the day of randomization, we will examine neurobiological surrogate markers involving psychophysiology (startle) and neuropsychological testing.

F. Study period II: 12-Week Randomized, Double-Blind, Placebo-Controlled Trial

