1. DNA

We will draw DNA on all consenting subjects to evaluate whether carriers of identified risk alleles are associated with response or non-response to voritoxetine.

2. mRNA

We will draw 12 mls of blood at baseline and at week 12 to evaluate the expression of HPA-related mRNA expression.

3. Neurophysiology: Startle Testing

3a. Conditioning sessions. The following methods will allow us to assess fear acquisition, and conditional discrimination (learned safety), as well as the subjects' awareness of reinforcement contingencies in the experiment. The aversive stimulus (US) in these studies will be a 250 ms airblast with an intensity of 80 p.s.i. directed to the larynx as described in similar human fear conditioning studies (Grillon & Davis, 1997; Jovanovic et al. 2005). A compressed air tank connected to polyethylene tubing and controlled by a solenoid switch will emit the airblasts. The conditioned stimuli (CS's) used in the AX+/BX- session (A, B, C and X) will be different colored shapes; in the fear acquisition and extinction sessions the CS's will be neutral pictures. The CS's will be presented on a computer monitor. The pictures and colored shapes will be counterbalanced across subjects. The stimuli will be presented using SuperLab 3.0 for Windows (Cedrus, Inc.) and synchronized with the psychophysiological data acquisition using a DIO card (Measurements Computing, Inc). The psychophysiological data will be collected with Biopac MP150 (Biopac Systems, Inc.). Skin conductance will be acquired concurrently with acoustic startle.

3b. Acoustic startle. The acoustic startle response (eyeblink component) will be measured via electromyography (EMG) of the right *orbicularis oculi* muscle. Two 5 mm Ag/AgCl pre-gelled disposable electrodes will be positioned approximately 1 cm under the pupil and 1 cm below the lateral canthus. All resistances will be less than 6 kilo-ohms. EMG activity is acquired at a sampling rate of 1kHz, amplified and digitized. The startle probe (noise burst) will be a 108-dB [A] SPL, 40-ms burst of broadband noise with a near instantaneous rise time.

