***See specific criterion for effective birth control methods.**

Exclusion:

CRITERION	METHOD OF ASCERTAINMENT
1. Lifetime or current diagnosis of schizophrenia or other psychotic disorder, dementia, bipolar disorder.	MINI and Clinical Evaluation
2. Subject is currently participating in another clinical trial in which s/he is or will be exposed to an investigational or non-investigational drug or	Clinical Interview

Updated **January 22, 2019**

device, or has done so within the preceding month.	
3. Subject has a prior unsuccessful trial of Vortioxetine at 20 mg/day or higher for 8 weeks or more	History
4. Current evidence or history of significant unstable medical illness or organic brain impairment, including stroke, CNS tumor, demyelinating disease, cardiac, pulmonary, gastrointestinal, renal or hepatic impairment that would likely interfere with the action, absorption, distribution, metabolism, or excretion of Vortioxetine. History of moderate or more severe TBI will also be exclusionary.	Medical chart review, clinical interview, physical exam, and laboratory testing
5. Patients who in the investigator's judgment pose a current suicidal or homicidal risk	Clinical Interview
6. DSM-5 substance abuse or dependence within the past 90 days. Subject has a positive urine toxicology test for illegal substances.	History, Urine Toxicology
7. Diagnosis of anorexia nervosa or bulimia in the past year.	MINI, History
8. Subject has a documented history of hepatobiliary disease including a history of, or positive laboratory results for hepatitis (hepatitis B surface antigen and/or hepatitis C antibody), AND clinically significant hepatic enzyme elevation, including any one of the following enzymes greater than 3 times the upper limit of normal (ULN) value (ALT, AST, ALP), or total bilirubin > 1.5 x ULN, unless consistent with presumed or diagnosed Gilbert's disease	History, Laboratory testing
9. Subject has taken systemic corticosteroids within 2 weeks of the Randomization Visit	History

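### Appendix A permits episodic oral steroids in Study Period I, where Exclusion 9 bars them, and no rule keeps them away from the week-12 HPA-related mRNA draw

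*Combined protocol and SAP*

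**What the plan says.** Appendix A carries the title "Drugs Allowed (Y) and Drugs not Allowed (N) for Study Periods I and II". Its oral steroid row is Y for episodic and N for chronic use. The row has no footnote, although the thyroid supplement row has one with a timing condition.

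Exclusion 9 (section VIII.B) applies where "Subject has taken systemic corticosteroids within 2 weeks of the Randomization Visit".

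Section V.A places Study Period I on Days -7 to -1 and says of its testing: "These visits will be conducted over a 7-day period prior to the day of randomization". Section V.E agrees: "which will be scheduled within one week of the day of randomization". At Day 0, "All subjects who continue to meet eligibility criteria will be randomized to one of two groups".

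On the biological samples, section V.J item 2 says: "We will draw 12 mls of blood at baseline and at week 12 to evaluate the expression of HPA-related mRNA expression". Section V.A and the Schedule of Events put the baseline sample at Visit 2 (Day 0) and the second at Visit 9. Exploratory Aim 3 asks "whether treatment with Vortioxetine alters gene expression patterns differentially in treatment responders and non-responders".

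**The concern.** There are two separate points.

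**Period I.** Site staff checking a concomitant drug would naturally turn to Appendix A. It tells them that a short oral steroid course is acceptable during pre-treatment testing. Exclusion 9 makes the same patient ineligible a few days later. The protocol does not say which text takes precedence. At stake are a screen failure, an eligibility deviation, or repeated startle and neuropsychological testing.

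**Period II.** The mRNA samples are taken to study HPA-related expression, which is where a corticosteroid course could plausibly matter (the documents do not quantify any effect). The baseline draw is in effect preceded by 14 steroid-free days, because Exclusion 9 is anchored to the same visit. The week-12 draw has no such interval. Aim 3 then compares responders with non-responders, a split that randomization does not balance. Uneven steroid use shortly before Visit 9 could therefore look like a response-related change in expression.

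**Working it through.** The plan gives no figure of its own on this point, so the check compares day windows and then illustrates size under stated assumptions.

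**1. Overlap in Period I.** Day 0 is randomization. Period I is Days -7 to -1. Reading the two weeks inclusively, Exclusion 9 bars Days -14 to 0. Overlap: 7 of 7 days.

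**2. Consequence of a Period I dose.** For a dose on Day -k (k = 1 to 7), the first randomization day with the dose outside the bar is Day 15 - k.
- k = 7: Day 8. k = 1: Day 14. The delay is 8 to 14 days.
- A test done on Day -j (j = 1 to 7) is then 15 - k + j days old. Minimum: 15 - 7 + 1 = 9. Maximum: 15 - 1 + 7 = 21.
- The limit is 7 days, so the test is always too old. If a dose exactly 14 days earlier were acceptable, each figure would fall by one day and the conclusion would stand.

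**3. Is the week-12 draw covered by any other text?**
- The on-treatment ban in V.F covers psychotropic drugs.
- The only hold before an assessment, also in V.F, is three days for diphenhydramine before startle or neuropsychological visits.
- The VIII.A statement on medication that interferes with biological assessments and the PI-judgment clause in Exclusion 10 are entry rules.
- Appendix A bars chronic oral steroids but permits episodic use.

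Required steroid-free days: 14 before the baseline draw, 0 before the week-12 draw.

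**4. Can the existing record identify exposure?** Visit 9 falls on Day 84 ± 3, that is Days 81 to 87, so a 14-day look-back starts between Day 67 (81 - 14) and Day 73 (87 - 14). Concomitant medication is recorded at Visits 2 to 10. Visit 7 is at the latest Day 59 (56 + 3), so the Visit 8 and Visit 9 entries cover the whole look-back.

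**5. Illustration of size.** Assumptions, none from the documents except the 60%: 30 vortioxetine patients; 60% respond (18 v 12; the abstract's ceiling for SSRIs) or 30% respond (9 v 21); each course shifts expression change by 1 to 2 SD. Bias = courses × shift / size of the group holding them.
- 18 v 12, courses in the smaller group: one gives 1/12 to 2/12 = 0.08 to 0.17 SD; two give 2/12 to 4/12 = 0.17 to 0.33 SD.
- 9 v 21, courses in the smaller group: one gives 1/9 to 2/9 = 0.11 to 0.22 SD; two give 2/9 to 4/9 = 0.22 to 0.44 SD.

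False-positive rate of a two-sided 5% t test with no true difference (100,000 simulated trials per case), by where the courses fall:
- One in the smaller group: about 5% to 6% (18 v 12) or 6% to 7% (9 v 21).
- Two in the smaller group: about 6% to 10% (18 v 12) or 8% to 14% (9 v 21).
- One or two in the larger group: about 4% to 6%.
- One in each group: about 3% to 5%.

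If placement is unrelated to response, two courses both fall in the smaller group with probability (12/30)(11/29) = 15% or (9/30)(8/29) = 8%.

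**The case against.** The strongest reply on Period I is that both texts apply, so the stricter one governs, and eligibility is rechecked at Day 0. That largely stands. A reader might infer that the baseline mRNA sample is contaminated. The documents do not support this, because a patient who took a steroid in Period I should not be randomized. It is also true that a patient who needs steroids in Period I is ineligible with or without a footnote. The footnote prevents only a dose taken, or a visit continued, because Appendix A appeared to allow it.

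On week 12, the reply is that the outcome is exploratory, chronic use is already barred, and neither the rate of steroid use nor its effect on expression is given. Two checks in section VII.B could also help: the assessment of covariates that differ between response groups, and the inspection of histograms and boxplots for outliers, with transformation or nonparametric methods as options. These protect only in part. The covariate check does not name steroid use, and an outlier check would not reliably reveal a shift of 1 SD.

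A reader might also take the 14% above as the expected error rate. It is a corner case: two courses, both in a group of nine, each with an assumed 2 SD shift. Most other placements leave the rate near or below 5%.

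Finally, discarding samples to remove a probably small bias costs precision. That is a fair point, and a sensitivity analysis that keeps the flagged samples answers it.

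**Conclusion.** Both points hold, and both are minor. The oral steroid entry in Appendix A is wrong for Study Period I: all 7 days conflict with Exclusion 9. The consequence is an avoidable screen failure or deviation, with the 8-to-14-day delay and out-of-window testing shown above. In Period II the entry permits a course just before an HPA-related draw, and nothing else in the protocol limits it. This could distort the exploratory responder comparison by an amount that the documents do not allow anyone to estimate.

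This rests on reading the oral steroid row as systemic corticosteroids (the ordinary sense, though the row does not define the term), on an inclusive two-week bar, and, for the second point, on the assumption that a short course alters HPA-related expression.

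It would be wrong to extend the point to the efficacy result. Nothing here affects the CAPS-5 analysis, the power statement or patient safety.

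**What to change.** (a) Footnote the oral steroid row of Appendix A: *Not allowed in Study Period I (see Exclusion 9).*

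(b) Add to section V.F or V.J: *Non-essential systemic corticosteroids are avoided in the 14 days before the actual Visit 9 mRNA draw.* The 14 days are borrowed from Exclusion 9 and are an assumption. Count back from the draw date itself, because Visit 9 has a ±3-day window and may be split over two days.

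(c) If a course is medically needed in that window, give it, and keep the patient in the trial and in all CAPS-5 analyses. Flag the week-12 mRNA sample from the concomitant-medication record before expression data are linked to response. Leave it out of the main gene-expression analysis and include it in a sensitivity analysis.

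The change needs one footnote and a short rule, with no new visit, test or form. The downside is possibly a few samples lost from the main exploratory analysis. In an 18 v 12 comparison (two-sided 5%, 80% power), losing 1, 2 or 3 of the 12 raises the detectable difference from d = 1.08 to 1.11, 1.15 or 1.19.

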Appendix B. Description of Scales

Brief Assessment of Cognition in Schizophrenia (BACS)

The Brief Assessment of Cognition in Schizophrenia (BACS) is a clinician-rated instrument that measures cognitive function. The domains of cognitive function that are assessed by the BACS include verbal memory, working memory, motor speed, attention, executive functions and verbal fluency. It is designed to require about 30 min of testing time. BACS A will be performed at V1 and Version B will be performed at V9.

UCSD Performance-Based Skills Assessment- Brief Version (UPSA-B)

The UCSD Performance-Based Skills Assessment (UPSA-Brief) is a role-play test designed to evaluate a person's functional capacity in two selected areas of basic living skills. The UPSA-Brief (UPSA-B) was developed as an abbreviated alternative to the full version of the UPSA ([Mausbach et al., 2007](#)) and contains 2 of the original 5 subscales of the full UPSA (i.e., finance and communications subscales), which allows for shorter administration time (10–15 minutes) and reduced reliance on testing props. An UPSA-Brief Total Score (range = 0–100) is then obtained by summing the subscale scores.

Clinical Global Impressions Improvement Scale (CGI-I) and Severity Scale (CGI-S)

The CGI-I (Guy 1976) is a clinician-rated instrument that measures the degree of the patient's improvement. It is a 7-point scale where 1 = very much improved; 4 = no change; and 7 = very much worse. Baseline for assessing improvement for the CGI-I ratings will be the patient's clinical status at Visit 3. The CGI-S is a similar clinician-rated instrument that measures the overall severity of the patient's illness as compared to the overall study population. It is also a 7-point scale where 1 = normal, not at all ill; 4 = moderately ill; and 7 = among the most extremely ill patients.

Clinician-Administered PTSD Scale (CAPS-5)

The CAPS is a structured clinical interview designed to assess the essential features of PTSD as defined by the DSM-5. The CAPS can be used to provide categorical ratings of diagnostic status as well as a quantitative index of symptom severity. The CAPS-5 Past-month version to be used in this study will include 22 items that assess the DSM-5 symptoms of PTSD during the screening visit and 20 items for all post screening visits, with each item scored from 0-4. Scores reflect an integration of each symptom's severity and frequency. The total score range is 0-80. Higher scores reflect a greater degree of symptoms severity.

Childhood Trauma Questionnaire (CTQ)

The CTQ (Bernstein, 2003) is a 28-item self-report instrument that assesses childhood trauma in the following areas: physical, sexual and emotional abuse and physical and emotional neglect. Each item is rated on a scale of 1 (never true) to 5 (very often true). The 5 subscales are then totaled, with scores ranging from 5-25 for each traumatic category.

Columbia Suicide Severity Rating Scale (CSSRS)

The CSSRS (Posner et al., 2007) is a brief, standardized, clinician-administered measure that uniquely assesses the essential information (behavior, ideation, lethality and severity) and distinguishes between suicidal occurrences and non-suicidal self-injury. The CSSRS is composed of 3 questions addressing suicidal behavior and 5 questions assessing the severity.

Emory Treatment Resistance Interview for PTSD (E-TRIP)

The E-TRIP (Dunlop et al. 2014) is a clinician administered measure that assesses the level of treatment resistance in an individual with PTSD by evaluating past treatments and their

effectiveness, symptom onset, and primary symptoms. All past treatments are recorded and evaluated through 8 questions to determine whether the past treatment received an adequate trial and to determine the efficacy of any past adequate trials.

Frequency, Intensity, and Burden of Side Effects Rating (FIBSER)

The FIBSER (Wisniewski et al., 2006) is a self-report measure used to quantify the overall side effect burden a patient is experiencing over the previous 7 days, used in combination with the PRISE. It uses 3 global ratings on a 7-point Likert-type scale to estimate: 1) the frequency of side effects; 2) the intensity of side effects the patient believes stem from the study treatment; and 3) the overall burden or degree of interference in day-to-day activities and functioning due to side effects. The form takes less than 5 minutes to complete.

Hollingshead Four Factor Index of Social Status

The Hollingshead is a self-report measure assessing the socio-economic status (SES) of the participant as well as the participant's parents. The participant indicates the level of education obtained by their father, mother, and self using a scale ranging from 1 (less than 7th grade completed) to 7 (Graduate degree); in addition, the occupation of each of the three people is also indicated along the scale, where 1 is equivalent to a farm or day laborer, and 9 is a senior manager or professional. The raw scores obtained for each individual are weighted (and in the case of the parents, averaged), yielding total Hollingshead scores for the participant and the parents.

Life Experiences Survey

The LES (Sarason et al, 1978) is a 43 item scale that lists numerous events which individuals may experience and call for social readjustment. Subjects are asked to indicate events which they have experienced during the previous reporting period and whether these events were perceived as positive or negative. Additionally, subjects are asked to rate on a 7-point scale the degree of impact these events have on their lives. From these responses it is possible to derive three life change scores: positive, negative, and total.

Montgomery-Asberg Depression Rating Scale (MADRS)

The MADRS (Montgomery and Asberg 1979) is a 10-item instrument used for the evaluation of depressive symptoms in adults and for the assessment of any changes to those symptoms. The estimated time to administer this scale is 20 minutes. Each of the 10 items is rated on a scale of 0 to 6, with differing descriptors for each item. These individual item scores are added together to form a total score, which can range between 0 and 60 points.

Pittsburgh Sleep Quality Index (PSQI)

The PSQI (Buysse et al., 1989) is composed of 19 self-rated questions and 5 questions rated by a bed partner (if available). The self-administered scale contains 15 multiple-choice items that inquire about frequency of sleep disturbances and subjective sleep quality and 4 write-in items that inquire about typical bedtime, wake-up, sleep latency and sleep duration. The PSQI generates seven scores corresponding to sleep domains. Each component score ranges from 0 (no difficulty) to 3 (severe difficulty). The component scores are summed to produce a global score (Range 0-21). A PSQI score >5 is considered to be suggestive of significant sleep disturbance. Most patients can complete the PSQI in 5-10 minutes.

The PTSD Checklist for DSM-5 (PCL-5)

The PCL-5 (Blevins et al. 2015) is a 20-item self-report measure that assesses the 20 DSM-5 symptoms of PTSD. All items are answered on a 5 point scale from 0 (not at all) to 4 (extremely). Scoring can be done to measure overall symptom severity or cluster symptom

severity by dividing the questions into the following groups: Cluster B (items 1-5), Cluster C (items 6-7), Cluster D (items 8-14), and Cluster E (items 15-20).

The Patient Rated Inventory of Side Effects (PRISE)

The PRISE (Rush et al., 2004) is a 7-item self-report assessment of side effects in the following symptom domains: gastrointestinal, heart, skin, nervous system, eyes/ears, genital/urinary, sleep, sexual functioning, and other. Each domain has multiple symptoms which may be endorsed, and for each domain the patient rates whether or not the symptoms are tolerable or distressing. The time frame evaluated is the past 7 days. The form takes less than 5 minutes for the patient to complete.

Quick Inventory of Depressive Symptomatology-Self Report (QIDS-SR)

The QIDS (Rush et al., 2003) is a 16-item self-rated instrument designed to assess the severity of depressive symptoms present in the past seven days. The 16 items cover the nine symptom domains of major depression, and are rated on a scale of 0-3. Total score range from 0 to 27, with ranges of 0-5 (normal), 6-10 (mild), 11-15 (moderate), 16-20 (moderate to severe), and 21+ (severe).

Sheehan Disability Scale (SDS)

The SDS (Leon et al 1997) is a patient-rated instrument designed to assess the impact of perceived problems on work productivity, social/leisure activities, and family life/home responsibilities. The Sheehan Disability Scale consists of 3 questions rated on a visual analog scale (0 to 10). Higher scores represent greater impairment of activity.

Mini International Neuropsychiatric Interview (MINI)

The MINI is an abbreviated neuropsychiatric diagnostic interview. It examines all of the conditions that are included as both inclusion and exclusion criteria in this trial. The MINI generates diagnoses with high reliability and is easy to train raters to administer with high fidelity. We will use modules A, and C through P in this study to evaluate the inclusion and exclusion criteria. Module B for Suicidality will be excluded, as the CSSRS will be performed at screening and every study visit from randomization onward.

REFERENCES

- American Psychiatric Association (2004): Practice guideline for the treatment of patients with acute stress disorder and posttraumatic stress disorder. *Am J Psychiatry* 161 (11): suppl): 3-31.
- Benjamini Y, and Hochberg Y. (1995) Controlling the False Discovery Rate: a practical and powerful approach to multiple testing. *JRSS-B*;57(1):289-300.
